**Measurement of Exposure and Outcome****a. Independent variables /exposure of study**

The module on nutrition education and WASH will be implemented such as;

1. Nutrition education: 12 Sessions will be planned for nutrition education

2. WASH education and practices: 4 sessions will be planned for education and hands-on practices for WASH especially handwashing and personal hygiene
3. Deworming will be administered before and after the intervention

**b. Dependent variables/Outcome of study**

1. Body Mass Index: All school going 6- 8 grade adolescents will undergo anthropometric measurements such as height, and weight (BMI). The measurement will be taken at baseline and end line by using WHO standard growth chart.
2. Micronutrients: Blood sample will be collected twice (baseline and end line) from a subset of 108 adolescents (54 intervention group,54 control group). The blood samples will help to assess the impact of intervention on micronutrient deficiencies (Iron, Zinc, Calcium, CBC, Vitamin D)
3. Physical examination: Physical examination like hair, skin, nail, eye (bitot spot), mouth (dental caries), and goiter will be assessed for micronutrient deficiencies at baseline and end line.
4. Knowledge, attitude, and practices regarding nutrition and WASH: a structured questionnaire will be used to collect data on nutrition and WASH-related indicators. The survey will be administered at baseline and end line. The indicator assessed will be adolescent health status and knowledge, attitude, and practices regarding nutrition and WASH practices.

**Research Question**

1. What is the effect of school-based nutrition education and water, sanitation, and hygiene intervention in improving nutritional status among early adolescents?
2. What is the impact of school-based nutrition education and water, sanitation, and hygiene intervention in reducing the prevalence of malnutrition among early adolescents?

## **Objectives of the study**

### **Primary objective**

To determine the efficacy of school-based nutrition education and water, sanitation, and hygiene intervention to improve nutritional status among early adolescents.

### **Secondary objective**

To measure the impact of school-based nutrition education and water, sanitation, and hygiene intervention on micronutrient levels among early adolescents.

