## Summary

Globally, one of the major risk factors for adolescent morbidity is considered Malnutrition. Worldwide adolescent age group 10-19 is increasing and they are at increased risk of malnutrition-related diseases resulting in high morbidity and mortality. Asian countries are suffering from the double burden of malnutrition including Pakistan. The risk factors that contribute to malnutrition in the population include unsafe drinking water, poor sanitary conditions, lack of proper waste disposal facilities, poor health awareness, and poor nutrition and hygiene. However, studies have shown that nutrition education, and water, sanitation, and hygiene (WASH) programs in schools are effective strategies to promote the health status of adolescents (girls and boys). The primary objective of this study is to determine a school-based nutrition and WASH education intervention to improve nutritional status among early adolescents. The randomized control trial (RCT) study design will be chosen for this study. This study will be carried out in Gojra public schools, in Punjab. The study participants will be 6-8 grade school-going adolescents (girls and boys), their mothers/immediate caretakers, and school teachers. The data collection methods that will be used for the study are surveys, focus group discussions (FGDs), and through observation. Anthropometric measurements and specified micronutrient levels of adolescents will be measured at baseline and end line. The intervention will consist of skill-based nutrition and WASH education for the adolescents along with deworming and micronutrient supplementation. Workshops based on nutrition and WASH will be arranged for school teachers. This study will be carried out over one year with two-time data collection (baseline, and end line). Data will be analyzed by using SPSS and transcription. The expected outcome of the study would be that the implementation of identified nutrition and WASH strategy is effective to generalize in the poor nutritional status population in schools. It will show the promising benefit of education and WASH intervention, in reducing the cases of

early adolescent malnutrition. Through the findings of the study, we can bring the revolution at the micro-level targeting the community to modify the curriculum of this age group.

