2. In the RCT phase, baseline assessment of the school-going adolescents will be conducted (knowledge, attitude, and practices (KAP) regarding healthy diet and WASH practices, along with biochemical markers (Blood complete picture, Zinc, Calcium, and Vitamin D level) in subset of 180 participants from total adolescent's target study population. Furthermore, intervention focusing multi components strategies like nutrition education, deworming, Water, Sanitation, and Hygiene will be implemented for 6, 7, and 8 grade school going early adolescents. For the Adolescents mothers/Immediate care taker cooking recipe books will be provided in the local context based on Pakistan dietary guidelines. Workshop will be arranged for school teachers to train them as master trainer. In the end line of the study, KAP evaluation and biochemical, markers will be done to assess the effectiveness of the intervention.
3. Dissemination phase or research uptake

Pakistan has significantly high incidence of malnutrition, which needs to be explored and addressed in early adolescents. Poor nutritional status in children leads to lot of physical and mental problems during this phase of life and afterword. Healthy Nutrition result in better growth and development during this period and is a second window of opportunity for catch up growth who have already experienced stunting (Bundy,2018 & WHO,2014). According to Hossen, “well-nourished adolescents at present can make optimal use of their skills, talents, and energies and be healthy, responsible citizens and parents of healthy babies” (Bhutta,2014 & Hossen,

2016). Hence, for their physical and mental development a good nutrition has a major role to play (Bundy et al., 2018).

Therefore, this study is designed to assess the effect of Nutrition education and water, sanitation, and hygiene intervention on school going early adolescent girls and boys in Gojra, Pakistan and to suggest ways how to overcome this health issue.

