Adolescents can contribute health of not only themselves but of their families and communities as a whole. The adaptive capabilities of adolescents make them more experimental, exploratory, and risk-taking, which in turn makes this age very appropriate to carry the studies which ultimately improve all aspects of their lives (Dick,2015).

The findings of this study will evaluate the knowledge, attitude, and practices of school adolescents regarding nutrition and WASH. Previous studies have focused on the nutrition intervention of under 5 years of age children or lactating and pregnant women; However, the present study will focus on multicomponent (nutrition, WASH, and deworming) intervention for school-going adolescents. This will be the first kind of its study conducted in a Pakistan setting. The results of this study will serve as a valuable guide for school management and health educators to plan suitable nutrition and health programs. This study will also offer recommendations for school management to adopt similar interventions for nutrition and WASH technique. This will also help them to repeat the same program for other target groups at school or community level. It will also encourage government and other stakeholders for the development of programs and policies related to nutrition and health at schools, districts and province levels. The present study will also add new knowledge to existing practices regarding nutrition and health of adolescents group.

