## **Framework**

For this study, a socio-ecological approach will be adopted because to change the behaviors of individuals permanently, changes in the environment has to take place (Wang, 2016). Based on the work of Urie Brofenbrenner, Lori Heise & McLeory in 1998 offered a theory-based framework for understanding the multi-layered and interactive effects of personal and environmental factors that determine behaviors such as smoking, physical activity, nutrition, sexual activity, and intermediate health promotion. This framework consists of five levels that are used in different setting at different levels. These levels include **intrapersonal**,

**Interpersonal, Institution, Community, and Policy. (Fig 1).** Regardless of topic, setting, and time period, most of the studies describe intrapersonal or interpersonal level activities with easily measurable objectives, while community and policy level activities are much less due to training of the health educators or resources to plan and implement institution, community, or policy level programs. However, few studies showed school-based intervention used three or more levels. (Level, 2002 & Golden, 2012). Furthermore, this model not only influence the health behavior of the target population, but also for the execution of health/ nutrition education, and WASH practices (Golden, 2012.) Therefore, this study will use the school health environment, school nutrition and WASH program, and family and community involvement based on the socio-ecological model to design the intervention at all levels.

[figure not shown]
**Intrapersonal:** At intrapersonal level knowledge, attitude, and practice regarding nutrition and WASH will be assessed. Skill-based education will be provided to the adolescents regarding healthy diet and WASH. Furthermore, monitoring of micronutrient levels and, deworming will be carried out.

**Interpersonal:** At the interpersonal level, involvement of mothers/immediate caretaker, teachers and school management and nutritionist will be ensured. Perception of the adolescent's mother/immediate caretaker and teachers will be assessed regarding nutrition and WASH practices. Peer lead, "adolescent to adolescent" approach will be used to develop a friendly environment to train the adolescents.

**Institution level:** Modification of the school environment, module development for focus areas and change in the school curriculum will be worked out.

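### The aims credit nutrition education and WASH, but the intervention also includes deworming and daily micronutrient tablets, and the arm description leaves the tablets out

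*Protocol*

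**What the plan says.** **The question.** The Summary states: "The primary objective of this study is to determine a school-based nutrition and WASH education intervention to improve nutritional status among early adolescents". The Purpose, Hypothesis, Research Question and Objectives sections use the same terms. The alternative hypothesis goes further and names the route: malnutrition is to fall through nutrition education and WASH practices. The secondary objective is "To measure the impact of school-based nutrition education and water, sanitation, and hygiene intervention on micronutrient levels among early adolescents". The Introduction closes by saying that "this study is designed to assess the effect of Nutrition education and water, sanitation, and hygiene intervention".

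**The intervention.** The Summary also says: "The intervention will consist of skill-based nutrition and WASH education for the adolescents along with deworming and micronutrient supplementation". The activity table (Detail of project activities) and the Intervention section repeat both additions, with one tablet daily for three months.

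**The arms.** Study design gives the intervention arm education, WASH and deworming, with no mention of tablets. Control schools receive routine education, free health screening at start and end, a health camp at the end and, if funds allow, a safe-water facility.

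**The expected conclusion.** The Summary says of the study: "It will show the promising benefit of education and WASH intervention".

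**The concern.** A trial with two arms that differ in several respects estimates the joint effect of those differences. The hypotheses and objectives here ask about two of the components, while the intervention contains at least four.

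The mismatch is sharpest for the secondary objective. Its outcome is blood micronutrient levels, measured at baseline and end line in a subset, and one of the unnamed components is a micronutrient tablet. Followed as written, the trial would answer a question about education and WASH with a contrast that also contains tablets and deworming. The Summary already words the conclusion that way. The section on sustainability plans to recommend the teaching module to policymakers for the curriculum, so an effect of the whole package could be used to support adopting education alone.

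A second problem follows. Study design, where the arms are defined, omits a component that other sections treat as part of the intervention. The protocol has no single list of what each arm receives.

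**Working it through.** No arithmetic is involved beyond counting. The check compares what the aims name with what the intervention sections contain.

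**Step 1: components named in the aims.**

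| Statement | Education and WASH | Deworming | Tablets |
|---|---|---|---|
| Purpose of the study | yes | no | no |
| Hypothesis, null | yes | no | no |
| Hypothesis, alternative | yes | no | no |
| Research Question 1 | yes | no | no |
| Research Question 2 | yes | no | no |
| Primary objective | yes | no | no |
| Secondary objective | yes | no | no |

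Count: 1 + 2 + 2 + 2 = 7 statements. All 7 name education and WASH; none names deworming or tablets.

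**Step 2: components named where the intervention is described.**

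| Section | Education and WASH | Deworming | Tablets |
|---|---|---|---|
| Summary | yes | yes | yes |
| Detail of project activities | yes | yes | yes, daily for three months |
| Intervention | yes | yes | yes, daily for three months |
| Exposure of the study | yes | no | yes, three months |
| Measurement of Exposure and Outcome, part a | yes | yes | no |
| Study design, intervention arm | yes | yes | no |

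Three sections give all components. The two exposure lists each omit what the other includes. Study design agrees with neither the Summary nor the Intervention section.

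**Step 3: what the contrast can answer.** The activity table addresses the tablets to study participants without naming an arm, so each possible allocation should be considered.

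- *Tablets and deworming in the intervention arm only.* The contrast is education + WASH + deworming + tablets against control. The text implies this allocation: tablets are listed as an exposure and under the intervention, control schools are described as without the intervention, and the control list names neither tablets nor deworming.
- *Tablets in both arms, deworming in the intervention arm only.* The contrast is education + WASH + deworming against control. It still does not isolate education and WASH. The Introduction itself cites evidence that deworming improved growth and anemia, and a complete blood count is among the planned measurements.
- *Tablets and deworming in both arms.* Only here would the aims match the contrast. Study design rules this out as the text stands, because it places deworming in the intervention arm and names none for control.

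Under neither allocation compatible with Study design's placement of deworming can a between-arm difference be assigned to education and WASH.

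**The case against.** **Package trials are legitimate.** This stands. Nothing is wrong with testing a combined intervention against a control condition, and the outcome and analysis sections already speak neutrally of the effect of the intervention. A reader might infer that the design is flawed or needs more arms. The documents do not support that; only the wording of the question and the component lists is at fault.

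**Education and WASH may be a short name for the package.** No aim says alone or only, and the Summary defines what the intervention consists of. This is a fair reading of the purpose and objectives. It fails for the alternative hypothesis, which names the route of effect, and it sits badly with the Summary's expected conclusion. It is also strained for the secondary objective, whose outcome is micronutrient levels.

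**The lists are not all meant to be complete.** This partly stands. The Introduction's description, "intervention focusing multi components strategies like nutrition education, deworming, Water, Sanitation, and Hygiene will be implemented", is open-ended, and part a of the measurement section also introduces its list as examples. The Framework's remark that "monitoring of micronutrient levels and, deworming will be carried out" describes one level of a model, and the health-camp text lists topics to reinforce. None of these should be counted as a firm conflict. In Significance of the study, "the present study will focus on multicomponent (nutrition, WASH, and deworming) intervention for school-going adolescents" is background prose. The firm conflict is Study design against the Summary, activity table and Intervention section; the two exposure lists also need reconciling.

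**A reader will find the tablets anyway.** This stands. The Summary and Exposure of the study mention supplementation before Study design is reached. It would overstate the matter to say that the protocol hides the tablets; the risk arises when Study design is read by itself.

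**The intervention is provisional.** The protocol says that it will be finalized after the formative assessment. That affects when the lists should be reconciled, but does not remove the present contradiction.

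**Conclusion.** The point holds as an internal inconsistency between the aims and the intervention. All seven aim statements name education and WASH, three sections describe a wider package with deworming and micronutrient tablets, and the arm description omits the tablets. A difference in blood micronutrient levels would be an effect of the package and cannot be credited to education and WASH. The same caution plausibly applies to malnutrition and BMI, and less clearly to knowledge, attitudes and practices.

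The conclusion assumes that at least deworming differs between the arms, as Study design says. That tablets also differ is strongly implied but never stated outright.

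A reader might infer that the tablets would inflate the result by some amount, or would raise particular measured levels. The documents do not support either: the tablets' composition is not given, and the share of any effect due to each component is unknown. No size of bias is claimed. The matter should be corrected before the trial's conclusions are drawn, but it does not undermine the comparison itself.

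**What to change.** 1. Reword the purpose, both hypotheses, both research questions and both objectives to the effect of the combined package actually given, compared with the control condition set out in Study design. Routine schooling would be the wrong comparator label, because control schools also get health screening, a health camp and possibly a water facility.
2. State that effects will not be attributed to nutrition education or WASH alone, and align the Summary's expected conclusion with this. The matching sentences in the Summary and Introduction should follow.
3. A possible secondary objective: *To measure the effect of the combined school-based package, compared with the control condition described under Study design, on micronutrient levels in early adolescents; effects will not be attributed to nutrition education or WASH alone.*
4. Once the intervention is finalized after the formative phase, reconcile Exposure of the study, Measurement of Exposure and Outcome, Study design, Detail of project activities and Intervention into one component list by arm. State outright which arm receives tablets and which receives deworming. This review does not say which components should be given.

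The cost is wording only: design, sample, measurements and analysis are unchanged.

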## **Methodology**

### **Study design**

A randomized control trial (RCT) will be chosen to see the results of school-based nutrition education and WASH intervention in early adolescent girls and boys in Gojra, Pakistan. RCT is a type of experimental design in which participants are randomly assigned to either the treatment or the control group, whereas they are not assigned randomly in the other type of experimental design such a quasi-experiment (Handley, 2018). Random assignment in RCT neutralizes factors (other than the independent and dependent variables) that directly infer cause and effect, and also avoids any possibility of selection bias in the trial (Kendall, J. (2003). Moreover, randomization also reduces the risk of unmeasured confounding that bias the study's conclusions (Axelrod, 2006).

This study meets the criteria of RCT which are;

- i. Randomization
- ii. Control group compared to the intervention group
- iii. Manipulation of the variables

In this study, a prospective, comparative experiment will be performed under controlled conditions with random allocation of the participants to both the intervention and control groups.

In the control group, the early adolescents will receive the routine education with free health screening (at the start and end of the study), participation in a health camp at the end of the study, and If the financial resources permit then a safe drinking water facility will be provided at school level as an incentive whereas in the intervention group, intervention (Nutrition education, WASH practices, and deworming) will be applied to the group participants.

### **Study Setting**

For this study, public schools (boys and girls) in Gojra will be selected. There are 40 public schools (20 boys and 20 girls) in Gojra. We will invite the schools for study projects that fulfill the eligibility criteria (inclusion and exclusion criteria). From these willing schools, four public schools that are at least 1-2 Km away from each other (two boys and two girls) will be randomly selected via balloting. The inclusion criterion related to distance is intended to reduce contamination between schools of different arms. These four schools (boys and girls) will then be randomly assigned to either the school (one boy and one girl) with the intervention or to the school (one boy and one girl) without the intervention (Control school).

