### **Sample Size & Sampling Strategy**

The sample size was calculated by using PASS software. Sample sizes were estimated to change in nutritional status of early adolescent boys and girls. A sample size of 360 adolescents

(180 in each intervention and control group) will achieve 80% power assuming 42% malnutrition among students in the control arm and at least 6% reduction in the intervention arm having 90 students from each school at a two-sided 5% level of significance.

To assess the micronutrient levels (Iron, Zinc, Calcium, CBC, and Vitamin D) through a blood sample, a subset of 108 adolescents 6-8 grade school going adolescents (54 intervention group, 54 control group) from this total sample size (360) will be selected through random selection.

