### Data analysis plan

Quantitative variables will be described by means and standard deviations whereas median with interquartile range will be mentioned for qualitative variables. Frequencies and percentages will be calculated for the knowledge, attitude, and practices of adolescents regarding nutrition and WASH. The comparison between intervention and control at baseline and end line will be performed by using paired t-test and Chi-square. For the variables that are not normally distributed, a nonparametric test McNamara will be used. Binary logistic regression and multiple linear regression will be used to assess the effect of intervention. All the statistical analyses will be conducted using SPSS version 23. A p-value less than 0.05 will be considered statistically significant.

Descriptive	Inferential

 
• Mean, SD Normally distributed
 
• Median, interquartile range Skewed distribution
 
• Percentages and frequencies of knowledge, attitude, and practices
 
	
 
• Chi-Square-McNamara knowledge, attitude, and practices
 
• T- test paired Continuous variables
 
• Binary logistic regression and multiple linear regression
 
• Proportion changes - chi-square Observational checklist
 

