**Intervention**

The intervention will be planned based on a socio-ecological model and health-promoting school framework. School health environment, health education, health services, and nutrition programs will be focused in the intervention stage of the study.

Based on the formative assessment, the module will be developed in consultation with Nutritionist, the research team, and recent literature. For the validity of the module, expert opinions will be taken from the nutritionist, school education, and WASH experts. Two to three workshops will be arranged for school teachers to train them as master trainers who are teaching 6 to 8-grade school-going adolescents. Sixteen sessions (one session per week) will be arranged on nutrition education and water, sanitation, and hygiene for adolescents. Micronutrient tablets will be administered to adolescents for three months daily through school teachers. Moreover, 6-8 grade adolescents will be dewormed before and after the intervention. In addition, Cooking recipes in the local language will be shared with the adolescent's mother/immediate caretakers through adolescents. Different strategies will be used in the study sessions like demonstrating and showing videos on hand washing, role play, quiz etc.

During the intervention phase, there are no such risks involved to the study participants except their valuable time. Due to deworming and micronutrient supplementation, there may be temporary dizziness, nausea, headache, constipation, and dark color stool along with discomfort from prick for blood drawing from adolescents. To reduce the temporary side effects of deworming administration, the researcher will advise them to keep adequately hydrated themselves and take the micronutrient supplementation tablet. Reassurance regarding drawing

the blood samples will be done. The existing referral system will be identified and utilized if needed

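### Four single-sex schools are randomised, but the Protocol describes allocation of participants and tests the intervention at student level with no allowance for school, so p-values are too small if same-sex schools differ

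*Protocol*

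**What the plan says.** - **Unit of randomisation.** Protocol, Study Setting: four single-sex public schools, two for boys and two for girls, are drawn by ballot. "These four schools (boys and girls) will then be randomly assigned to either the school (one boy and one girl) with the intervention", and the remaining boys' and girls' school serve as controls. A minimum distance between schools is imposed to limit contamination between arms.
- **Unit as described elsewhere.** Protocol, Study design, speaks of an experiment "with random allocation of the participants to both the intervention and control groups".
- **Sample size.** Protocol, Sample Size & Sampling Strategy (RCT phase): 180 per arm, 80% power, 42% malnutrition in the control arm and a 6% reduction, "having 90 students from each school at a two-sided 5% level of significance". It gives no ICC and no design effect.
- **Analysis.** Protocol, Data analysis plan (RCT phase): "The comparison between intervention and control at baseline and end line will be performed by using paired t-test and Chi-square". "Binary logistic regression and multiple linear regression will be used to assess the effect of intervention". "A p-value less than 0.05 will be considered statistically significant". It names no school effect, mixed model, GEE or cluster-robust variance.
- **Measurement and delivery.** On BMI: "The measurement will be taken at baseline and end line by using WHO standard growth chart". On delivery: "Micronutrient tablets will be administered to adolescents for three months daily through school teachers". Teachers also give the nutrition and hygiene sessions.

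**The concern.** A student-level chi-square or ordinary regression treats the 180 students in an arm as 180 independent pieces of evidence about the intervention. They come from two schools, and the intervention was assigned to schools. Students in one school share teachers, sessions, facilities and surroundings, so some similarity beyond sex is plausible. If it exists, the variance of the arm difference is larger than these methods assume. The 5% error rate is then not held, and any intervals are too narrow.

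Each arm has only one school per sex. Something that happens in one school during the year and has nothing to do with the intervention cannot be told apart from an intervention effect. The Protocol's Summary expects the result to support wider use of the strategy, so a false positive would have consequences.

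**Working it through.** **Inputs from the Protocol.** Four schools, two per arm, one per sex; m = 90 students per school; 42% against 36% (the 6% reduction read as percentage points); two-sided 5%. **Assumed, because the Protocol gives no values:** the residual ICC and the baseline/end-line correlation r.

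**1. The stated 80% power, before any clustering.** Pooled proportion 0.39.
- SE under the null = √(2·0.39·0.61/180) = 0.0514.
- SE under the alternative = √(0.42·0.58/180 + 0.36·0.64/180) = 0.0513.
- Power = Φ[(0.06 − 1.96·0.0514)/0.0513] = Φ(−0.79) ≈ 21%.

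The 80% is not reproduced. It would need 1,037 students per arm even if students were independent.

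**2. Error rate of the student-level end-line test.** Design effect DE = 1 + (m − 1)·ICC = 1 + 89·ICC. True rejection rate of a nominal 5% test = 2·[1 − Φ(1.96/√DE)].

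| Assumed residual ICC | DE | True rejection rate |
|---|---|---|
| 0.001 | 1.09 | 6.0% |
| 0.0025 | 1.22 | 7.6% |
| 0.005 | 1.45 | 10.3% |
| 0.01 | 1.89 | 15.4% |
| 0.02 | 2.78 | 24.0% |
| 0.05 | 5.45 | 40.1% |

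Beta-binomial simulation (400,000 runs, prevalence 42%, four schools of 90) gave 5.9%, 7.5%, 10.2%, 15.3%, 24.0% and 40.8%.

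**3. Correlation due only to sex.** Assume 47% malnutrition in boys and 37% in girls, mean 42%. The raw within-school ICC is 0.05²/(0.42·0.58) = 0.0025/0.2436 ≈ 0.010. Each arm has one school of each sex, so this part cancels in the arm comparison, and the chi-square test rejects a true null about 4.8% of the time in simulation. The ICC in step 2 must therefore be read as variation between schools of the same sex.

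**4. What a school-level analysis can do.** Take baseline-to-end-line change per school, with baseline 42% in all schools and end line 42% (control) or 36% (intervention).
- Control: Var_con = 2·0.42·0.58·(1 − r)/90.
- Intervention: Var_int = [0.42·0.58 + 0.36·0.64 − 2r·√(0.42·0.58·0.36·0.64)]/90.
- SE of the arm difference = √[(Var_int + Var_con)/2].

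At r = 0 this is √[(0.00527 + 0.00541)/2] = 0.073. Power from the noncentral t with noncentrality 0.06/SE, and no residual school variation:

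| Assumed r | SE | Power, 1 df (critical t 12.7) | Power, 2 df (critical t 4.30) |
|---|---|---|---|
| 0 | 0.073 | 7% | 8% |
| 0.5 | 0.052 | 8% | 11% |
| 0.8 | 0.033 | 12% | 19% |
| 0.9 | 0.023 | 16% | 32% |

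One df applies if schools are compared within sex, two if by arm only. Residual school variation lowers these figures further. With one school of each sex per arm there are 2 × 2 = 4 possible allocations, so the smallest two-sided randomisation p-value is 2/4 = 0.5.

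**The case against.** **Any within-school correlation inflates the error.** A reader might infer this, but the design does not support it. The schools are single-sex and each arm has one of each, so correlation that comes only from sex is harmless, as step 3 shows. The Introduction reports more underweight among boys than girls in Punjab, so correlation of this kind is to be expected. Only variation between same-sex schools matters.

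**All the named tests are affected.** This is also too strong. The paired t-test and the McNemar test (printed as McNamara) compare before with after within students and do not test the arm difference. The inflation concerns the chi-square comparison of arms and the regressions. Offering a paired test as a comparison of arms is a separate matter.

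**Baseline measurement removes stable school differences.** This is true and important, but school-specific change remains. As an illustration, take a between-arm student-level test of change, which the plan does not name. If school-specific change has an assumed SD of 3 percentage points, the test would reject a true null about 7%, 9% and 15% of the time at r = 0, 0.5 and 0.8. With no school-specific change it holds 5%.

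**The Study design wording is only loose.** This is partly fair, since Study Setting follows at once and is clear about schools. But the loose wording agrees with an analysis that treats students as the unit.

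**The analysis plan may handle this.** A separate statistical analysis plan, not shown, could override these methods. The Protocol does not leave the choice open, however: it names the methods and the threshold.

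**The sizes are assumed, and only for malnutrition prevalence.** This stands. Nothing here quantifies knowledge, attitude and practice scores or the 108-student blood subset.

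**Conclusion.** The point holds for residual variation between same-sex schools, or for school-specific change over the study. Under either, the student-level between-arm p-values are too small. For the unadjusted end-line test the true error rate is about 6–8% at a residual ICC of 0.001–0.0025, and runs from 10% to 40% between 0.005 and 0.05. These ICCs are assumptions; if the residual ICC is zero, the nominal 5% is kept.

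The limitation that does not depend on any assumed ICC is structural: with one school per sex per arm, school-specific change is confounded with the intervention. A random effect or GEE would not cure that, because only 1 or 2 degrees of freedom are available at school level.

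The documents do not show that every within-school correlation does harm, nor that the before-after tests are inflated by this mechanism.

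**What to change.** 1. **Study design and Sample Size & Sampling Strategy (RCT phase):** describe the trial as cluster-randomised by school, one boys' and one girls' school per arm, and replace the phrase about allocating participants.
2. **Sample Size & Sampling Strategy (RCT phase):** remove the 80% power statement. Otherwise it would stand beside an admission of very low power.
3. **Data analysis plan (RCT phase):** base inference about the intervention on baseline-to-end-line change per school. Fix the degrees of freedom in advance: 1 df (critical t 12.7) for a comparison within sex, or 2 df (critical t 4.30) for arm only. Report all four school results. State that student-level p-values that ignore school will not be used to claim efficacy.
4. **Summary:** label the effect estimate preliminary and not grounds to generalise.

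**Cost.** This changes wording and simplifies the analysis; no extra schools or students are required. Intervals become much wider: at 1 df with no residual school variation, the simulated median 95% half-width is about 64, 42, 28 and 21 percentage points at r = 0, 0.5, 0.8 and 0.9. Power for 42% against 36% is very low on either choice of degrees of freedom, and four schools can make no confirmatory efficacy claim. The 1-df test is itself not exact: because the counts are discrete, it rejected a true null 5.4–7.6% of the time in simulation over the same range of r. A confirmatory claim would need more schools per arm, which is a separate design decision.
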